4.5. Visit Windows

Analysis visit windows will be defined for analysis purposes and for summary tables presented by visit. Both scheduled and unscheduled assessments will be considered as valid assessments for analysis.

Analysis visit labels will be assigned to each record based on the study day windows relative to the date of the planned single dose of study drug.

To support the definition of analysis window, study day compared to the date of the planned single dose is calculated as:

Date of assessment – Date of the planned single dose +1, for assessments done after planned single dose of study drug;

Date of assessment – Date of the planned single dose, for assessments done before planned single dose of study drug.

Table 1: Analysis Visit Window (General)

TIMING OF ASSESSMENT	VISIT NAME TO DISPLAY FOR ANALYSIS	TARGET DAY	ANALYSIS WINDOW (STUDY DAY)
Visit 1	Baseline		≤ -1
Visit 2	Baseline		1 (Pre-dose)
Visit 3	Start of 12-Week Treatment	14	Post-baseline – 22
Visit 4	Week 2 of 12-Week Treatment	28	23 – 36
Visit 5	Week 4 of 12-Week Treatment	42	37 – 57
Visit 6	Week 8 of 12-Week Treatment	70	58 – 85
Visit 7	Week 12 of 12-Week Treatment	98	86 – last dose day* + 7
Visit 8	Follow-Up after 12-Week Treatment	112	\geq last dose day* + 8

Note: This table shows assessments for vital signs, blood sampling for serum total and individual bile acids, urinalysis, and clinical chemistry.

EOT=end of treatment.

*The later of (Last dose day, EOT visit day) will be used.

Table 2: Analysis Visit Window for Specific Assessments

ASSESSMENT(S)	TIMING OF ASSESSMENT	VISIT NAME TO DISPLAY FOR ANALYSIS	TARGET DAY	ANALYSIS WINDOW (STUDY DAY)
BLOOD SAMPLING FOR FGF-19	Visit 2	Baseline		≤ 1 (Pre-dose)
	Visit 3	Start of 12-Week Treatment	14	Post-baseline – 29
	Visit 5	Week 4 of 12-Week Treatment	42	30 – 71
	Visit 7	Week 12 of 12-Week Treatment	98	72 – last dose day* + 7
BLOOD SAMPLING FOR C4	Visit 2	Baseline		≤ 1 (Pre-dose)

ASSESSMENT(S)	TIMING OF ASSESSMENT	VISIT NAME TO DISPLAY FOR ANALYSIS	TARGET DAY	ANALYSIS WINDOW (STUDY DAY)
	Visit 3	Start of 12-Week Treatment	14	Post-baseline – 29
	Visit 5	Week 4 of 12-Week Treatment	42	30 – 71
	Visit 7	Week 12 of 12-Week Treatment	98	≥ 72
BLOOD SAMPLING FOR BIOMARKERS	Visit 2	Baseline		≤ 1 (Pre-dose)
	Visit 3	Start of 12-Week Treatment	14	Post-baseline – 29
	Visit 5	Week 4 of 12-Week Treatment	42	30 – 71
	Visit 7	Week 12 of 12-Week Treatment	98	72 – last dose day* + 7
	Visit 8	Follow-Up after 12-Week Treatment	112	\geq last dose day* + 8
URINE SAMPLING FOR INDIVIDUAL AND TOTAL BILE ACIDS	Visit 2	Baseline		≤ 1 (24-hour Pre-Dose period)
	Visit 3	Start of 12-Week Treatment	14	Post-baseline – 29
	Visit 5	Week 4 of 12-Week Treatment	42	30 – 71
	Visit 7	Week 12 of 12-Week Treatment	98	72 – last dose day* + 7
	Visit 8	Follow-Up after 12-Week Treatment	112	\geq last dose day* + 8
HEMATOLOGY	Visit 1	Baseline		≤ -1 (Pre-dose)
	Visit 3	Start of 12-Week Treatment	14	Post-baseline – 22

ASSESSMENT(S)	TIMING OF ASSESSMENT	VISIT NAME TO DISPLAY FOR ANALYSIS	TARGET DAY	ANALYSIS WINDOW (STUDY DAY)
	Visit 4	Week 2 of 12-Week Treatment	28	23 – 36
	Visit 5	Week 4 of 12-Week Treatment	42	37 – 57
	Visit 6	Week 8 of 12-Week Treatment	70	58 – 85
	Visit 7	Week 12 of 12-Week Treatment	98	86 – last dose day* + 7
	Visit 8	Follow-Up after 12-Week Treatment	112	≥ last dose day* + 8
Pruritus NRS lead question	Visit 1	Baseline		≤ -1
COAGULATION	Visit 1	Baseline		≤ -1
	Visit 3	Start of 12-Week Treatment	14	Post-baseline – 29
	Visit 5	Week 4 of 12-Week Treatment	42	30 – 71
	Visit 7	Week 12 of 12-Week Treatment	98	72 – (last dose day* + 7)
12 LEAD ECG	Visit 1	Baseline		≤ -1
	Visit 2	Baseline		1 (Pre-dose)
	Visit 5	Week 4 of 12-Week Treatment	42	Post-baseline – 71
	Visit 7	Week 12 of 12-Week Treatment	98	72 – (last dose day* + 7)
ENDOSCOPIC BILIARY DILATION DATA	Visit 2	Baseline		≤1 (Pre-dose)
	Visit 7	Week 12 of 12-Week Treatment	98	Post-baseline – (last dose day* + 7)

ASSESSMENT(S)	TIMING OF ASSESSMENT	VISIT NAME TO DISPLAY FOR ANALYSIS	TARGET DAY	ANALYSIS WINDOW (STUDY DAY)
PHYSICAL EXAMINATION	Visit 1	Baseline		≤ -1
	Visit 2	Baseline		1 (Pre-dose)
	Visit 5	Week 4 of 12-Week Treatment	42	Post-baseline – 71
	Visit 7	Week 12 of 12-Week Treatment	98	72 – (last dose day* + 7)
	Visit 8	Follow-Up after 12-Week Treatment	112	\geq last dose day* + 8
FAECAL CALPROTECTIN	Visit 2	Baseline		≤ 1 (Pre-dose)
	Visit 3	Start of 12-Week Treatment	14	Post-baseline – 22
	Visit 4	Week 2 of 12-Week Treatment	28	23 – 36
	Visit 5	Week 4 of 12-Week Treatment	42	37– 57
	Visit 6	Week 8 of 12-Week Treatment	70	58– 85
	Visit 7	Week 12 of 12-Week Treatment	98	86 – (last dose day*+7)
	Visit 8	Follow-Up after 12-Week Treatment	112	\geq last dose day*+8
FIBROSCAN	Visit 1	Baseline		≤ -1
	Visit 3	Start of 12-Week Treatment	15	Post-baseline – 29
	Visit 5	Week 4 of 12-Week Treatment	43	30 – 71
	Visit 7	Week 12 of 12-Week Treatment	99	72 – (last dose day* + 7)

ASSESSMENT(S)	TIMING OF ASSESSMENT	VISIT NAME TO DISPLAY FOR ANALYSIS	TARGET DAY	ANALYSIS WINDOW (STUDY DAY)
	Visit 8	Follow-Up after 12-Week Treatment	113	\geq last dose day* + 8

Note: This table shows assessments for specific visits.

C4=7 α -hydroxy-4-cholesten-3-one; FGF-19=fibroblast growth factor 19; NRS= numerical rating scale; ECG= electrocardiogram; EOT=end of treatment .

*The later of (Last dose day, EOT visit day) will be used.

5. Patient Disposition

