AFP = (alpha-fetoprotein); C4 = (7 α -hydroxy-4-cholesten-3-one); CA 19-9 = carbohydrate antigen 19-9; ECG = electrocardiogram; ERCP = endoscopic retrograde cholangiopancreatography; ELF = enhanced liver fibrosis; EOT = End-of-Treatment; FGF-19 = fibroblast growth factor 19; FSH = follicle stimulating hormone; hsCRP = high-sensitivity C-reactive protein; MIST = metabolites in safety testing; MMP = matrix metalloproteinase; MRCP = magnetic resonance cholangiopancreatography; NRS = numerical rating scale; WOCBP = women of childbearing potential; WONCBP = women of non-childbearing potential.

- ^a The EOS visit is required 14 (+/-2 days) following Visit 7 or the date of last dose for patients who prematurely discontinue treatment.
- ^b An EOT visit must be performed as soon as possible after premature drug discontinuation. If the patient is terminated after Visit 2 due to high exposure, an End-of-Study Visit should be conducted.
- ^c Any new medical or surgical history findings after the Screening Period (Visit 1) will be reported as an AE, not as patient medical or surgical history.
- ^d To include height (Screening only), weight, temperature, pulse, and systolic and diastolic blood pressure. Vital sign measurements should be taken before A3907 administration.
- ^e The last dose of study drug is planned to be administered at Visit 7. The first of the BID doses will be administered at the clinic and patients will be instructed to take the second of the BID doses at home, 12 hours after the first dose was received.
- ^f Patients will return all unused study drug at Visit 4, Visit 5, Visit 6, and Visit 7. The study site staff will count all returned drug, assess compliance, and record drug accountability.
- ^g Patients will fast for 4 hours prior to all pre-dose blood samples.

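### An early stopper's off-drug End-of-Study sample matches both a treatment-period window and Follow-Up, and SAP 4.5 has no rule to choose between them

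*SAP*

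**What the plan says.** SAP 4.5 labels records by study day: "Analysis visit labels will be assigned to each record based on the study day windows relative to the date of the planned single dose". All records are eligible: "Both scheduled and unscheduled assessments will be considered as valid assessments for analysis".

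- **Fixed windows.** In Table 1 (vital signs, serum bile acids, urinalysis, clinical chemistry) the Visit 3 to Visit 6 windows are day ranges that do not refer to last dose, for example "Week 4 of 12-Week Treatment 42 37 – 57" and "Week 8 of 12-Week Treatment 70 58 – 85". Table 2 treats its Visit 3 to Visit 6 rows in the same way. For biomarkers, urine bile acids and FibroScan, Week 4 runs from Day 30 to Day 71.
- **Windows tied to last dose.** Week 12 in Table 1 is "86 – last dose day* + 7". Follow-Up is everything from last dose day + 8. The asterisk on last dose day is explained in a footnote: "The later of (Last dose day, EOT visit day) will be used".
- **Visits after stopping.** Footnotes a and b of the protocol's Schedule of Assessments put End of Study 14 (±2) days after the last dose for early stoppers and ask for an EOT visit as soon as possible. For the exposure check they say: "If the patient is terminated after Visit 2 due to high exposure, an End-of-Study Visit should be conducted".

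SAP 4.5 has no precedence rule, no on-treatment condition, and no rule for several records in one window.

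**The concern.** One set of windows is fixed by calendar and the other moves with last dose. For a completer the two sets do not overlap. For someone who stops early, Follow-Up opens while a fixed treatment-period window is still running, so one record satisfies both. A programmer must then pick a label or count the record at both visits, and two programmers could produce different tables from the same text.

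The summaries at stake are the by-visit ones: bile acids and serum biomarkers (SAP 8.2), and liver biochemistry with 95% confidence intervals at each post-baseline visit (SAP 9.2). With about 6 patients per arm, one off-drug value in an on-treatment row carries visible weight.

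The protocol also generates extra records of this kind. Section 9.3.6.4 requires weekly monitoring after permanent discontinuation for safety, and section 9.3.6.1 allows liver tests two or three times a week.

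**Working it through.** The plan has no figure of its own to reproduce. The check is window arithmetic.

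**Inputs**

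- L = later of last dose day and EOT visit day (SAP 4.5 footnote). Base case: EOT on the last-dose day, so L is the last dose day.
- Follow-Up opens at L + 8 (SAP Tables 1 and 2).
- End of Study = last dose + 14, ±2 (protocol Schedule of Assessments, footnote a).
- The last fixed window ends on Day 85 (Table 1 Week 8; also haematology and faecal calprotectin) or Day 71 (Table 2 Week 4 for biomarkers, urine bile acids, FibroScan and physical examination).

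**Step 1: when does End of Study match two windows?** It always matches Follow-Up in the base case, since L + 14 > L + 8. It also matches a fixed window when L + 14 is no later than the end of the last fixed window:

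- Table 1 set: L + 14 ≤ 85, so L ≤ 71.
- Table 2 set: L + 14 ≤ 71, so L ≤ 57.

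| End of Study at | Table 1 set: L up to | Table 2 set: L up to |
|---|---|---|
| L + 12 | 73 | 59 |
| L + 14 | 71 | 57 |
| L + 16 | 69 | 55 |

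The windows themselves overlap for L up to 85 − 8 = 77 (Table 1) or 71 − 8 = 63 (Table 2).

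**Step 2: how much of the treatment period is this?** On SAP numbering the 12-week period starts on Day 15 and a completer's last dose is on Day 99. Early last-dose days therefore run from 15 to 98, which is 84 days. Affected: 71 − 15 + 1 = 57 of 84 (Table 1 set) and 57 − 15 + 1 = 43 of 84 (Table 2 set). These count days; they are not a forecast of how many patients stop.

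**Step 3: examples with prompt EOT**

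| Last dose | End of Study | Fixed window matched | Follow-Up opens |
|---|---|---|---|
| Day 43 | Day 57 | Week 4 (37–57), Table 1 | Day 51 |
| Day 50 | Day 64 | Week 8 (58–85), Table 1 | Day 58 |
| Day 50 | Day 64 | Week 4 (30–71), Table 2 biomarkers | Day 58 |
| Day 99 | Day 113 | none | Day 107 |

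**Step 4: weekly liver tests.** With last dose and EOT on Day 43, tests on Days 50, 57, 64 and 71 fall in Week 4, Week 4, Week 8 and Week 8. Follow-Up opens on Day 51, so the last three also match Follow-Up.

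**Step 5: late EOT.** With last dose on Day 80 and EOT on Day 90, L = 90. Week 12 in Table 1 then runs from Day 86 to Day 97 and Follow-Up opens on Day 98. The EOT sample (10 days off drug) and the End-of-Study sample on Day 94 (14 days off drug) are both Week 12 only. Likewise, last dose Day 43, EOT Day 50 and End of Study Day 57 give Week 4 only, because Follow-Up opens on Day 58.

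**Step 6: patient stopped after the single dose.** L = 1 and the End-of-Study sample is on Day 15. It matches *Start of 12-Week Treatment* (post-baseline to Day 22 or 29) and *Follow-Up after 12-Week Treatment* (from Day 9). The physical examination has no Visit 3 row, so it matches Week 4 and Follow-Up.

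**Step 7: after a cap.** If the fixed windows also end at last dose + 7, the Day 50 case has Week 4 ending on Day 57, no Week 8, and Follow-Up from Day 58. The Day 64 sample is then Follow-Up only.

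**The case against.** The strongest reply is that little of consequence depends on this. The primary endpoint is TEAE incidence, which does not use these windows, and no hypothesis test is planned. The secondary bile acid and liver-test endpoints are changes to Week 12. For those assessments the Week 12 window already closes at last dose + 7, so with a prompt EOT the End-of-Study sample stays out. The protocol asks for EOT as soon as possible, so a 10-day delay would be unusual, and its schedule shows Week 12 and EOT as one column. All of that stands, and it confines the problem mainly to intermediate visits.

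A reader might also infer more than the documents support:

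- **That the windows disregard dosing altogether.** They do not. The Follow-Up lower bound and the Week 12 upper bound use last dose, apart from C4, whose Week 12 is Day 72 onward with no cap.
- **That C4 and FGF-19 are double-labelled.** Neither is sampled at Visit 8 or has a Visit 8 row.
- **That patients stopped by the exposure check mix off-drug with on-drug values.** At Visit 3 everyone is about 14 days past a single dose and is sampled pre-dose, so the dosing state is the same. The fault is a label for a period never entered.
- **That the protocol expects the pharmacodynamic effect to be gone by End of Study.** Section 5.5 says that any benefit is not expected to last beyond the study. It says nothing about effect 14 days after last dose, and the half-life value is redacted.
- **That the SAP prescribes double counting.** It does not; it leaves the choice open.

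The SAP's restriction to patients who actively entered the 12-week period does not answer the point. It selects patients rather than records, and for bile acids, biomarkers and laboratory changes it applies to the baseline 2 tables only.

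**Conclusion.** The point holds as a fault in the window rules. Applied literally, they give two labels to an early stopper's End-of-Study sample for last doses up to Day 71 (Table 1 assessments, haematology, faecal calprotectin) or Day 57 (biomarkers, urine bile acids, FibroScan, physical examination). Safety follow-up tests can be affected in the same way. A late EOT visit can leave an off-drug sample with an on-treatment label only, and this is the one route by which the bile acid and liver-test Week 12 rows are affected.

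These limits assume EOT on the last-dose day and End of Study exactly 14 days later; the ±2-day window moves them by 2 days. How many patients are affected depends on early stopping, which the documents do not predict. One value is roughly a sixth of an arm's visit summary, and less if withdrawn patients are replaced. The direction and size of any shift in a mean cannot be derived from the documents. The amendment is worth making before the tables are programmed; nothing here threatens the primary analysis.

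**What to change.** Amend SAP 4.5 as follows:

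1. End every on-treatment window, including C4 Week 12, no later than actual last dose day + 7, which is the allowance the SAP already uses for Week 12. Later records go to Follow-Up only.
2. Base both the cap and the Follow-Up start on last dose day, not on the EOT visit day.
3. State which record is used when several fall in one window.
4. Give post-single-dose records of patients who never entered the 12-week period a separate label, and keep those patients in the safety displays.

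The cost is table wording and programming. A few early-stopper values move from on-treatment visits to Follow-Up. For assessments with no Visit 8 row, such as C4 and FGF-19, a record beyond the cap has no summary row, so the SAP should say that it is listed only.

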9.3.6.4 Monitoring after Permanent Discontinuation of Study Drug Due to Safety

Once study drug is permanently discontinued for hepatic, gastrointestinal (e.g. diarrhoea), or other severe AE related to study drug, the patient will be monitored weekly until the laboratory and clinical parameters have normalised/stabilised.

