8.2. Pharmacodynamic analyses

Secondary and exploratory PD variables (bile acids, C4, FGF-19, autotaxin, ProC3, hsCRP, MMP7, MMP9, ELF score, and CA 19-9) will be analyzed descriptively for categorical and continuous data, as applicable. For continuous data, the relative and absolute change from baseline 1 at each post-baseline visit will be analyzed in addition to the actual values. 2-sided 95% CI of the mean for relative and absolute change from baseline 1, and actual values will be

presented along with descriptive statistics. Similarly, summary tables presenting relative and absolute change from baseline 2 for the 12-week treatment period will be presented. For categorical data, shift tables or frequency and percentages of patients will be presented as appropriate.

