9.2. Clinical Laboratory Evaluations

Clinical safety laboratory evaluations will be performed by a central laboratory. Samples will be collected for clinical laboratory evaluations at timepoints indicated in [Table 1](#) and [Table 2](#). Safety lab parameter like clinical chemistry and urinalysis ([Appendix 2](#)) will be presented from Baseline up to Follow-Up after 12-Week Treatment. Hematology will be presented at Baseline, Start of 12-Week Treatment up to Follow-Up after 12-Week Treatment. Coagulation will be presented at Baseline, Start of 12-Week Treatment, Week 4 of 12-Week Treatment and Week 12 of 12-Week Treatment.

Descriptive statistics for clinical laboratory values [chemistry, hematology, urinalysis, coagulation laboratory tests, LBTs including aminotransferase (ALT and AST), GGT, ALP, and total and direct bilirubin levels] will be presented. For LBTs, 2-sided 95% CI of the mean for relative and absolute change from baseline 1 to each post-baseline visit and the last visit, and actual values at each visit will be presented along with descriptive statistics. Relative and absolute changes from baseline 1 to each post-baseline visit and the last visit will also be presented for quantitative variables. For clinical chemistry assessments and urinalysis tests with quantitative results, baseline 1 is defined as the average of all Screening results and results on the day of the planned single dose if both results are available. Otherwise, baseline 1 will be defined as the last non-missing assessment prior to the study drug administration of planned single dose. For other laboratory parameters, baseline 1 is defined as the last non-missing assessment of that parameter prior to the study drug administration of planned single dose. For categorical variables (i.e., normal or abnormal findings, or qualitative clinical laboratory tests), a table of categorical values over time will be presented. Results of quantitative clinical laboratory values will be categorized as low, normal, or high according to laboratory range specifications. Shifts from baseline 1 to each scheduled post-baseline time point will be presented to show the number and percentage of patients in each category by parameter.

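### SAP 4.5 fixes the Visit 3 to 6 windows but opens Follow-Up on any study day, so an early stopper's off-drug End-of-Study record can carry a treatment-visit label with no rule to settle it

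*SAP*

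**What the plan says.** SAP 4.5 assigns visit labels by study day, not by nominal visit: "Analysis visit labels will be assigned to each record based on the study day windows relative to the date of the planned single dose". It also admits every record: "Both scheduled and unscheduled assessments will be considered as valid assessments for analysis".

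In SAP Table 1, Visit 3 runs to Day 22, and Visits 4, 5 and 6 are Days 23–36, 37–57 and 58–85. None of these depends on when the patient stopped drug. Visit 7 does: "86 – last dose day* + 7". Follow-Up is any day from "last dose day* + 8" onward, with no minimum study day. The asterisk is explained as "The later of (Last dose day, EOT visit day) will be used".

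Table 2 has the same structure with wider windows for biomarkers and urine bile acids: Visit 3 to Day 29, Visit 5 Days 30–71, Visit 7 from Day 72 to the same cap, then Follow-Up. FGF-19, C4, coagulation and ECG have no Follow-Up row. The C4 Week 12 window is Day 72 or later, with no upper limit.

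The labels feed the by-visit tables. For pharmacodynamic markers (SAP 8.2), "the relative and absolute change from baseline 1 at each post-baseline visit will be analyzed in addition to the actual values". For liver tests (SAP 9.2) the tables give the "2-sided 95% CI of the mean for relative and absolute change from baseline 1 to each post-baseline visit and the last visit".

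For early stoppers, footnote a of the protocol's schedule of assessments puts EOS 14 ±2 days after last dose. Footnote b asks for EOT as soon as possible after stopping, and section 7.1.1 places it at discontinuation.

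**The concern.** The Visit 7 cap suggests an intention to keep off-drug records out of treatment visits, but it was not carried to Visits 3 to 6. If a patient stops early, the EOS record is about two weeks off drug and can still lie inside a fixed treatment window. The same record also qualifies for Follow-Up. SAP 4.5, section 11 and the appendices give no precedence rule, and none for choosing among several records in one window. Naming Visit 8 beside Follow-Up in the timing column does not settle it, because the operative sentence assigns by study day.

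Two analysts following the SAP could therefore produce different by-visit tables. One could place an off-drug value in a Week 2, 4 or 8 mean change and its confidence interval, or count one record under two visits.

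**Working it through.** The plan states no figure to reproduce; the check applies the windows as written.

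**Inputs.** SAP study day = date minus single-dose date, plus 1. L is the last-dose day, taken over Days 15–98 (84 possible days of the 12-week period). EOS is on day L + d, with d = 12 to 16 (protocol footnote a). EOT is on day L + e. The documents give no number for e, so it is an assumption and is varied. The anchor is the later of last dose and EOT, which is L + e.

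**Conditions for the EOS record.**
- Follow-Up applies if L + d ≥ L + e + 8, that is d ≥ e + 8.
- A Table 1 treatment window (Visits 3–6) applies if L + d ≤ 85. For Table 2 biomarkers and urine bile acids the limit is 71.
- Week 12 applies if L + d ≥ 86 (Table 2: ≥ 72) and d ≤ e + 7.

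**Short EOT lag.** For the earliest EOS, d = 12, Follow-Up requires e ≤ 4. So with e from 0 to 4, every EOS record at 14 ±2 days is in Follow-Up. It is also in a treatment window when L ≤ 85 − d (Table 1) or L ≤ 71 − d (Table 2). Counting from Day 15:
- Table 1: 71 − d days, which is 59, 57 and 55 of 84 for d = 12, 14 and 16.
- Table 2: 57 − d days, which is 45, 43 and 41 of 84.

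At d = 14 the 57 Table 1 days split as follows: L = 15–22 gives Week 2 (8 days), L = 23–43 gives Week 4 (21), and L = 44–71 gives Week 8 (28). The 43 Table 2 days are 42 as Week 4 and 1 as Start of 12-Week Treatment.

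**Is EOS the only scheduled record under that label?** With EOT on the last-dose day and d = 14, an EOT record shares the Table 1 window for L = 37–43 and 58–71, which is 7 + 14 = 21 days. On the other 57 − 21 = 36 days, EOS is the only scheduled record. For Table 2, EOT shares the window on Day 15 and Days 30–57 (1 + 28 = 29), leaving 43 − 29 = 14.

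*Example:* last dose and EOT on Day 50, EOS on Day 64. The EOS record is both Week 8 (58–85) and Follow-Up (from Day 58). The EOT record on Day 50 falls in the Week 4 window.

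**Longer EOT lag.** With e = 7 and d = 14, Follow-Up opens at L + 15, so the EOS record has no Follow-Up label and there are 0 dual labels of 84. It carries a treatment label alone. That label is Week 12 for L ≥ 72 in Table 1 (98 − 72 + 1 = 27 of 84) and L ≥ 58 in Table 2 (98 − 58 + 1 = 41 of 84).

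**Patients stopped at the PK check.** L = 1 and EOS is on Days 13–17, all inside the Visit 3 window. With EOT by Day 5, Follow-Up opens by Day 13, so all 5 EOS days carry two labels. With EOT on Day 10 it opens on Day 18, so 0 of 5 do.

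**Assessments with no Follow-Up row.** There is no dual label, but an off-drug record keeps a treatment label. With last dose and EOT on Day 40, coagulation on Day 54 is Week 4 (30–71), and an unscheduled C4 on Day 75 would be Week 12.

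**Effect on a mean.** If one of 6 patients contributes an off-drug value and the others share a common change, the mean change is diluted by 0% (no reversal) up to 1/6 = 17% (full return to baseline). Both ends are assumptions.

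**The case against.** The strongest reply is that this is an uncontrolled, descriptive study of about 24 patients with no hypothesis test. The primary endpoint is TEAE incidence, the change endpoints are defined at Week 12, and patient listings are planned. All of that stands, and it limits the harm to by-visit summaries.

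Some stronger readings are tempting but unsupported.

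- *Most early stoppers will be mislabelled.* The counts are last-dose days, not patients. No dropout rate is given.
- *The Week 12 results are contaminated.* With EOS at 14 ±2 days and EOT within 4 days of last dose, the Visit 7 cap keeps EOS out of Week 12. That protection fails only when EOT trails last dose, or when EOS comes much earlier than footnote a allows. For C4 the cap is absent, but C4 is not scheduled at EOS, so only an unscheduled sample would be affected.
- *Weeks of post-discontinuation safety tests enter Week 8.* After a safety discontinuation, protocol 9.3.6.4 says "the patient will be monitored weekly until the laboratory and clinical parameters have normalised/stabilised". With last dose on Day 40, weekly tests on Days 61–82 would meet the Week 8 window. They fall after the EOS visit due on Days 52–56, however, and neither document says whether laboratory results after EOS enter the by-visit tables.
- *One cap cures everything.* Capping the early windows would leave later FGF-19, C4, coagulation and ECG records with no label at all, including the repeat INR values that hepatic monitoring calls for.

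**Conclusion.** The point holds in limited form. Applied as written, SAP 4.5 gives an early stopper's EOS record two labels over roughly two-thirds of possible last-dose days in Table 1 (57 of 84, 68%, at EOS +14) and half for Table 2 biomarkers and urine bile acids (43 of 84, 51%). This assumes EOT within 4 days of last dose and applies only where a Follow-Up row exists. A late EOT removes the duplicate but leaves the off-drug record with a treatment label alone, which can be Week 12. The PK-check duplicate also depends on an early EOT.

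The consequence is possible dilution and double counting in descriptive means and intervals in arms of about 6. The number of patients affected cannot be estimated from the documents. This should be corrected because the rule itself gives the wrong label and the correction is cheap; it does not threaten the trial's primary conclusion.

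**What to change.** Amend SAP 4.5 as follows.

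1. Label every EOS-visit record Follow-Up, whatever its study day. This also removes the Week 12 label that a late EOT would produce.
2. For assessments with a Follow-Up row, extend the existing cap (7 days after the later of last dose and EOT) from Visit 7 to Visits 3–6. Keep that anchor so that EOT values are retained. With item 1, each post-dose record then has one label, and dual-labelled EOS days fall from 57 and 43 to 0 of 84.
3. Cap the C4 Week 12 window as for FGF-19. For FGF-19, C4, coagulation and ECG, either add an unscheduled or Follow-Up category, or state that records beyond the cap are listed only.

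This does not settle which record is summarised when several on-treatment records share a window; one added sentence would. Some protocol and SAP passages put EOS within 14 days of last dose, whereas footnote a says 14 ±2 days. That is a separate, minor alignment.

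The cost is SAP wording and light reprogramming before database lock, with no extra visits. Some intermediate-visit cells lose an off-drug value (for example n = 6 becomes 5), and off-drug coagulation and INR values beyond the cap move to Follow-Up or to listings.
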